## INVESTIGATOR STUDY PLAN – Take a Break (H00007427)

stolen, there is minimal risk to participants. The recorder will be stored in a locked drawer in a locked office. Upon transcription of the interviews, the data will be stored within the UMMS Regulated Environment and saved within a password-protected folder created for this aim of the study. The list of participants will be stored separately from the transcribed interviews.

Data will not be released to other researchers. Data will be stored for 6 years.

Statistical Analyses: To preserve the power of randomization, all primary analyses will be on an intent-to-treat basis. However, secondary analyses will explore dose-response effects among those with variable levels of adherence to the intervention, as ascertained by survey. All analyses will be two-sided and alpha error will be set at 0.05. We will begin the statistical analysis by examining univariate statistics (means, medians, standard deviations and 95% confidence intervals) and distributions. We will examine the balance of participant characteristics by study groups and account for any imbalances in our multivariable analysis. As appropriate, group differences will be tested using chi-square tests of independence (categorical variables), Z-test or t-test (continuous variables) or the equivalent non-parametric tests depending on the distribution of the variables. In accordance with best practice, differences in baseline characteristics of the intervention and comparison groups will be established based on standardized differences, rather than on tests of statistical significance.

## INVESTIGATOR STUDY PLAN – Take a Break (H00007427)

- Hypothesis 1: The mean number of days abstinent will be greater in the intervention than in the control. Both groups will be observed for (t=) 14 days. If we assume X1 to be the number of days abstinent in the intervention group and X2 to be the number of days abstinent in the control group, then  $X1 \sim \text{Poisson}(t\lambda_1)$  and  $X2 \sim \text{Poisson}(t\lambda_2)$  where  $\lambda_1$  and  $\lambda_2$  are mean days of abstinence in the two groups. Our null hypothesis is that these two rates are similar. In order to test this hypothesis, we will first compute the number of days abstinent for each individual over the 14 days of the “Break” portion of the Marathon and obtain the mean number of days abstinent within each group. We will use the Z-test to test whether difference in the mean days of abstinence between the groups is statistically significant. If we find significant differences in the distribution of the characteristics of subjects in the two groups, then we will include them as covariates in a multivariable Poisson regression model with the number of days abstinent as our main outcome and group as the main independent variable.

## INVESTIGATOR STUDY PLAN – Take a Break (H00007427)

of instantaneous probability of an event in the two groups. A positive hazard ratio implies that the intervention group will have a shorter time to quit than the control group. We will express the risk estimates as hazards ratios, 95% confidence intervals, and p-values. As with the previous aims we will also assess model fit.

- Hypothesis 4: Point prevalent cessation measured at 6 months will be greater in the Take a Break intervention than in the control group. The main dependent variable is patient tobacco cessation rate. The primary independent variable is assignment to intervention or control group. We have designed a patient-level analysis around point prevalence cessation based on the following question “Do you currently smoke cigarettes (smoked even 1 puff in the last 7 days)?” We will use a two-sided chi-square test for equality of proportions to test whether the quit rates differ between the groups. If we need to adjust for any covariates, we will include them in a multivariable logistic regression model with smoking cessation as the outcome and group status as the main independent variable. Using mediation analysis, we will examine the potential mechanisms through which we anticipate the intervention may produce a beneficial effect.

Power Analysis: We will make every effort to maximize participant retention in the study. For our short-term evaluation, we do not expect high rates of attrition; however, we approximate that there will be about 15-20% attrition based on previous studies. Thus, although we plan to randomize 500, our power calculations for outcomes are based on 400 completing follow-up. We will monitor recruitment and retention, and inflate our sample as needed to achieve the resulting sample of 400 completing 6-months. We will estimate potential bias due to dropouts in our study and perform a series of sensitivity analyses to understand the extent of this bias. We will assess the extent of missing data by treatment group for each time point. Power calculations are based primarily on the two primary hypotheses (H1 and H3) and were conducted in the statistical software PASS. Again, power calculations are based on 400 subjects with complete data (even though we plan to randomize 500).

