### 3) Objectives

Take a Break (TAB) is a randomized trial designed to evaluate Nicotine Replacement Therapy (NRT)-sampling and a mHealth suite of apps. TAB is a time-limited self-efficacy and skills building experience for Motivation Phase smokers. TAB is designed to create a timeline within which motivation smokers will be encouraged to try a brief period of abstinence. Smokers in this Motivation Phase are relatively untapped in research available information. This project offers these smokers point-of-need technology support in the many components of the intervention.

Our Specific Aims are

[figure not shown]
- AIM 1: Refine the Take a Break mHealth tool and implementation program.
- AIM 2: Conduct a randomized trial of the effectiveness of Take a Break.
- AIM 3: Follow participants in the AIM 2 randomized clinical trial for 6 months to evaluate time to quit attempts, number of quit attempts, and 6-month biochemically verified point prevalent cessation.

The Take a Break intervention is designed to increase self-efficacy and support new skills for Motivation Phase smokers. We hypothesize that, compared with the NRT-only group, the Take a Break group will have a greater number of days abstinent during the ‘break’ period, a greater increase in self-efficacy at the end of the ‘break’ period, a lower time to first quit attempt, and a higher rate of quit at 6 months. This research study will also provide valuable insight into this population of smokers and increase our understanding of which tools may be effective in helping them quit smoking.

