### 5) Inclusion and Exclusion Criteria

For all Aims, we will include individuals 18 years and older who are identified as current smokers who are not preparing to quit, and are active in care within the UMMHC system, Northwell Health, VA Central Western MA (VACWM) and Reliant Medical Group (RMG). Active in care is defined as having at least two clinical visits in the past year. If an eligible participant does not already have a smart phone, one will be provided to them, free of charge, for the duration of their participation in the study.

- Exclusion Criteria: Those unwilling to sample nicotine lozenges or participate in the intervention will be excluded. All patients already on NRT will be excluded. All participants who have a FDA contraindication or cautions for nicotine lozenge use (pregnancy, breastfeeding, recent cardiovascular distress, or phenylketonuria) will be excluded. We have chosen to exclude patients with a diagnosis of depression, due to confounding factors.

Adults unable to consent, individuals who are not yet adults (infants, children, teenagers), and prisoners will be excluded from this study. The Food and Drug Administration (FDA) advises caution for nicotine lozenge use among women who are pregnant. Thus, women who are pregnant at the time of baseline will be excluded from the study. Those who are already participating in another smoking cessation study at the time of screening will also be excluded from the study.

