### RMG Recruitment Strategy:

**In-person Recruitment Strategy:** RMG will implement in-person screening at the time of visit. RMG will utilize the Epic Electronic Health Record (EHR) currently in production at practice sites to identify eligible subjects and obtain participation interest in real-time. Through this process, patients are screened for tobacco use by a Medical Assistant (MA) at the start of their visit. When patients report positive tobacco use, this information is flagged within the EHR and alerts the MA to inquire whether the patient might be interested in participating in the study. The EHR alert is a smart alert that only appears once if the patient is an active smoker age 19 and older who isn't pregnant, has English listed as their primary language, and hasn't been asked to participate in the study before. MA's will be trained on the objectives of the study, the inclusions/exclusion criteria, and the study activities and commitments of participants. The MA enters the response into Epic. Each morning the RMG Research Department will query Epic's Clarity Database to identify patients that expressed an interest in the study. This list of interested patients will then be forwarded to the RMG TAB study staff in order to identify eligible patients. Identified patients will be contacted by telephone within 48 hours of office visit by RMG study staff for screening of study inclusion criteria. During the screening call, the study staff member/recruiter will review the purpose of the study, answer any questions, assess for competency to provide verbal consent and assess study inclusion and exclusion criteria. Patients who screen-in and provide verbal consent will schedule an in-person appointment with RMG study staff to provide informed consent and be enrolled in the study. A total of three phone calls will be made over the course of 3 weeks from the initial contact. On the third call, study staff will leave a short voicemail message asking potential participants to call the RMG Research Department. If patients are not reached during these initial phone calls, an invitation letter (see RMG invitation letter) will also be sent asking potential participants to call the RMG study staff if still interested.

[figure not shown]

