## INVESTIGATOR STUDY PLAN – Take a Break (H00007427)

completion of the Training Challenge, players will be asked to set a goal for number of days abstinent during the Break challenge.

- *Week 2-3 The BREAK NRT-sampling experience and mHealth tools:* The Break is a two-week experience. During the Break, smokers are encouraged to initiate abstinence from smoking and maintain abstinence for as long as possible. Consistent with a motivational intervention, smokers will not be forced to initiate abstinence on the first day of their assigned Break period, but will earn points for each day they reply to the ecological momentary assessment through our two-way texting system. During the Break, smokers will be supported by our evidence-based and effectiveness-tested mobile health tools in the Game. At the end of the Break, players will meet once more with our study staff. All Intervention participants will receive gold, silver, or bronze level awards for participation and will be asked if they would like to set a quit date. Current smoking will be determined through self-report and verification with a carbon monoxide breath monitor. Smoking cessation verification will be performed at the study site they were recruited at during the participant's last in-person session.

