## INVESTIGATOR STUDY PLAN – Take a Break (H00007427)

### Take a Break Study Timeline by Study Aim (2 &3)

## INVESTIGATOR STUDY PLAN – Take a Break (H00007427)

### 11) Data and Specimen Banking

Data collection for this project includes web-based, telephone, and in-person methods for Aims 1, 2, and 3. (Table 3). All primary study data collected will be centralized and stored within the UMMS Regulated Environment. Paper copies of consent forms and data collection tools (baseline and follow-up surveys) will remain at the study-specific sites in a locked cabinet. Only CITI trained study staff will be able to access to primary study data. Data files cannot be transferred electronically outside of the regulated environment.

**Aim 1: Usability think-aloud interviews.** We will conduct usability interviews using the Morae software and laptops with full data encryption. The Morae recording will be transferred to a server in the UMMS IS regulated environment and removed from the laptops.

**Aim 1 + 2: Mini Pilot + RCT.** Surveys conducted on the telephone and in-person (see Table 3 for specific surveys) will be recorded within REDCap at the time of completion. TAB activity will be collected by UMMS web-based servers and stored within the UMMS IS regulated environment.

Table 3: Data Collected and Source

Variable	Source		Stage of Collection					
	EHR Registry	Baseline	App Metrics	Follow Up	Screening	Baseline	Intervention	Follow Up
Demographics (age, gender, race)	Y	Y	N	N	Y	Y	N	N
Level of Addiction (FTND)	N	Y	N	N	N	Y	N	N
Past Quit History	Y	Y	N	N	N	Y	N	N
Readiness to Quit	N	Y	N	Y	Y	Y	N	N
SES/Housing Stability	N	Y	N	N	N	Y	N	N
Depression (CES-D)	N	N	N	N	Y	N	N	N
Alternative Tobacco Use & e-cig	N	Y	N	Y	N	Y	N	Y
NRT Use	Y	Y	N	Y	Y	Y	N	Y
Alcohol/Illlicit Drug Use	N	Y	N	Y	N	Y	N	Y
Smoking in Household	N	Y	N	N	N	Y	N	N
Cessation Treatment Beliefs	N	Y	N	Y	N	Y	N	Y
Health Behaviors (exercise, sleep diet)	N	Y	N	Y	N	Y	N	Y
Health Literacy	N	Y	N	N	N	Y	N	N
Medical Comorbidities (SCQ)	Y	Y	N	N	Y	Y	N	N
Perceived Stress	N	Y	N	Y	N	Y	Y	Y
Provider Behavior	N	Y	N	N	N	Y	N	N
Religion	N	Y	N	N	N	Y	N	N
Self-efficacy (SEQ-12)	N	Y	N	Y	N	Y	N	Y
Smoking Urges (QSU)	N	N	Y	Y	N	N	Y	Y
Social Support/Family (mMOS-SS)	N	Y	N	N	N	Y	N	N
Technology Literacy	N	Y	N	N	N	Y	N	N
Triggers	N	Y	N	N	N	Y	N	N
Challenge Quiz Completion	N	N	Y	N	N	N	Y	N
Days Abstinent	N	N	Y	N	N	N	Y	N
Smoking Cessation*	N	N	N	Y	N	N	N	Y
(biochemically verified a 3wk, 6 months)								
Time to First Quit Attempt	N	N	N	Y	N	N	N	Y

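### Hypothesis 4 claims tobacco or smoking cessation but is scored on a cigarettes-only question, and carbon monoxide testing closes the gap only in part

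*Combined protocol and SAP*

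**What the plan says.** In section 12 (Data Management), Statistical Analyses, Hypothesis 4, the outcome is introduced as follows: "The main dependent variable is patient tobacco cessation rate". The patient-level analysis then rests on a single item: "Do you currently smoke cigarettes (smoked even 1 puff in the last 7 days". Later in the same paragraph the adjusted model is described "with smoking cessation as the outcome and group status as the main independent variable". The paragraph therefore carries two labels, tobacco cessation and smoking cessation, and one item that asks about cigarettes.

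Other sections bear on this:

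- **Entry.** Section 5 admits people "identified as current smokers who are not preparing to quit". Under the RMG strategy in section 7, "patients are screened for tobacco use by a Medical Assistant (MA) at the start of their visit". The RMG record alert is then limited to active smokers, and staff screen by telephone. Nowhere is cigarette smoking stated as a requirement.
- **Other products.** Table 3 in section 11 lists "Alternative Tobacco Use & e-cig" at baseline and at follow-up. Hypothesis 4 does not use it.
- **Verification.** Section 3 describes the Aim 3 endpoint as "6-month biochemically verified point prevalent cessation", and Table 3 marks cessation as verified at 3 weeks and 6 months. For the end of the Break, section 10 says: "Current smoking will be determined through self-report and verification with a carbon monoxide breath monitor".
- **Limits on verification.** Section 11 (Aim 3) restricts the test to participants who took the optional lozenges, and section 32 agrees. Section 10 lets participants who cannot attend at six months return the survey by post.

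**The concern.** An outcome should be scored by a rule that matches its name. Here the item is narrower than either label. Two kinds of participant can truthfully answer no while still smoking: a cigarette smoker who has moved to cigars or a pipe, and a person who smoked only cigars or a pipe from the start. The second would meet the self-report definition at entry.

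If such people are spread evenly across arms, both cessation rates rise and the difference shrinks. If switching is more common in one arm, part of the observed difference is product substitution. Because no rule says how the alternative-tobacco data enter the score, the choice could also be made after the data are seen. The choice of label matters too: under tobacco cessation a smokeless user is a failure, and under smoking cessation that person is not.

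**Working it through.** **1. Who is scored abstinent on the text as written.** The self-report item asks about cigarettes over 7 days. Someone who smokes only cigars or a pipe answers no. CO measures smoke exposure and is not specific to cigarettes, so such a person could fail a breath test. The check is incomplete in three ways: participants who did not use lozenges are not tested; no test is described for those who post the survey back; and Hypothesis 4 does not say what a CO result does to the score. For anyone untested, the cigarette item is the only scoring rule.

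**2. The plan's own power figure.** Inputs from section 12, Power Analysis, Hypothesis 4: 200 per group, 15% versus 26%, two-sided 0.05, pooled Z-test, stated power 80%. With p̄ = (0.15 + 0.26)/2 = 0.205:

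Power = Φ( [ (p2 − p1)√n − 1.96 √(2p̄(1 − p̄)) ] / √(p1(1 − p1) + p2(1 − p2)) )

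= Φ( [0.11 × 14.142 − 1.96 × 0.571] / 0.566 ) = Φ( (1.556 − 1.119)/0.566 ) = Φ(0.772) = 78.0%.

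Exact enumeration of the same test gives 78.6%. The difference detectable at 80% power is 11.3 points, which rounds to the stated 11. The figure is reproduced within rounding; 78% is the reference below.

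**3. Illustration, equal mis-scoring in both arms.** The documents give no rate of cigar or pipe use. Assume that 15% and 26% are the true smoking-cessation rates, that a share m of true non-quitters in each arm is scored abstinent, and that CO corrects none of them. The scored rate is p + (1 − p)m, and the difference becomes 11 × (1 − m) points.

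| m (assumed) | Control | Intervention | Difference (points) | Power |
|---|---|---|---|---|
| 0 | 15.00% | 26.00% | 11.00 | 78.0% |
| 2% | 16.70% | 27.48% | 10.78 | 74.0% |
| 5% | 19.25% | 29.70% | 10.45 | 68.2% |
| 10% | 23.50% | 33.40% | 9.90 | 59.3% |

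**4. Illustration, unequal mis-scoring.** Assume no true effect (15% in both arms) and m = 5% in the intervention arm only. The scored rates are 0.15 + 0.85 × 0.05 = 19.25% and 15%. With 200 per arm, the chance of a significant result favouring the intervention is about 20%, against a nominal 2.5% in that direction.

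**The case against.** The strongest reply is that six-month cessation is described elsewhere as biochemically verified, and that a CO test would expose a cigar or pipe smoker. That stands for anyone who is tested. A reader might infer that every cigar or pipe smoker counts as a quitter; the documents do not support this. The reply does not cover untested participants, and Hypothesis 4 gives a failed test no consequence.

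Second, the tobacco label appears once in Hypothesis 4 and may be a slip, since the rest of that analysis speaks of smoking cessation. That is plausible, but correcting it leaves an item that omits cigars and pipes.

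Third, a reader might take RMG's tobacco-use screen to mean that any tobacco user could enter, or that cigar-only smokers were enrolled. Neither follows. That screen belongs to one site and is narrowed to active smokers before the telephone screen. The telephone script is not in the documents and may ask about cigarettes. Table 3 calls other products alternative, which suggests that cigarettes are the reference. All that can be said is that the written criteria do not exclude a cigar-only or pipe-only smoker.

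Fourth, the illustrations rest on assumed shares, and the plan does not say how its 15% was defined. If that rate already came from a cigarette question, adding m counts the same people twice. Planned power would then be unaffected, and the issue would be what the rate means. This stands, and it is why the power figures are illustrations.

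Finally, Hypothesis 4 is not primary: Hypothesis 3 is labelled so, and the Power Analysis names Hypotheses 1 and 3.

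**Conclusion.** The mismatch is real. Participants who smoke only cigars or a pipe, or who switch to them, are scored abstinent on the Hypothesis 4 question unless a CO test catches them, and that test is limited in reach and has no stated role in the score. The data needed to separate them are already being collected.

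The size is unknown. The fall in power from about 78% to 74%, 68% or 59% rests on assumed shares of 2%, 5% and 10%, on 15% and 26% being true smoking-cessation rates, and on no CO correction. Where testing is done, the effect is smaller. The effect of unequal switching likewise depends on an assumed imbalance; nothing in the documents shows that one exists.

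The point concerns a named Aim 3 endpoint with its own power calculation, so it merits correction, but it does not touch the primary hypothesis. The documents do not support reading it as a reason to reopen eligibility.

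**What to change.** In Hypothesis 4, label the outcome smoking cessation throughout. Score a participant as abstinent only if they report no cigarettes and no other combustible tobacco in the last 7 days, using the Table 3 alternative-tobacco item collected at follow-up. The wording and recall window of that item are not shown. If its window differs for participants already followed, use it as collected in a pre-specified sensitivity analysis.

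Report e-cigarette and smokeless use among abstainers separately. Add a sensitivity analysis that excludes participants whose baseline data show no cigarette smoking. This is preferable to changing section 5: recruitment was under way, one site had stopped by June 2019, and two sites answer to their own ethics boards. A narrower criterion now would make earlier and later participants differ.

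This change does not settle how CO results and untested participants are scored; Hypothesis 4 needs its own rule for that.

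The cost is a slightly lower reported cessation rate and a small amount of extra analysis.

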## INVESTIGATOR STUDY PLAN – Take a Break (H00007427)

- Hypothesis 4: We assumed a control cessation rate of 15%, 48 a two-sided significance level of 0.05. A sample size of 200 in each group will achieve 80% power to detect a difference of 11% (quit rate in the intervention=26%) in quit rates between the two groups. This is based on a Z-test with pooled variance.

Data Security: We will handle data differently for UMMS, Northwell Health, VACWM and RMG smokers, per each institution's protocol. UMMS and RMG are covered under the same UMMS IRB docket while Northwell Health and VACWM have protocols independently reviewed by their own IRB. Table 4 summarizes data collection. There will be no transfer of patient data between study sites and UMMS prior to recruitment into study. Screening data collected for recruitment will be password protected and stored behind each study site's firewall. Patient contact information provided through the eRefer portal will be encrypted at rest and during transit using Secure Sockets Layer (SSL) standard security protocol. Each study site will have access to only its own identifiable patient data with the exception of UMMS study staff which will have access to all participant identifiable data. Once smokers are enrolled in the study, their intervention data will be stored on UMass servers. This will be done by entering the data directly into the UMMS REDCap database by study staff at each study site. This data will be stored in the regulated database servers and accessible through a secure form and a password-protected connection.

Table 4: Data Collection Source and Storage

Source	Collected From	Personal Identifiers	Collected By	Data Storage
Aim 1				
Think Aloud Usability	Smokers participating in the usability sessions at UMMS Technology usability lab	Yes (identifiers are collected and stored in encrypted form)	UMMS database server in the regulated environment	UMMS IS regulated environment
Mini pilot	Mini Pilot will match Aim 2 data collection plus an additional qualitative interview	Yes (identifiers are collected and stored in encrypted form)	See Aim 2 procedures. Qualitative interviews are directly entered into the regulated environment through a secure REDCap form	UMMS IS regulated environment
Aim 2 Recruitment				
Recruitment – UMMS	Smoker data will be collected from UMMS EHR and the eRefer portal	Yes (identifiers are collected and stored in encrypted form)	All data extracted from EHR will be stored in the regulated environment. Data collected from eRefer portal will be encrypted.	UMMS IS regulated environment
Recruitment – Northwell	Smoker data will be collected from Northwell EHR	Yes (identifiers are collected and stored in encrypted form)	All data extracted from EHR will be stored in the regulated environment	Northwell IS regulated environment
Recruitment – VACWM	Smoker data will be collected from VA EHR	Yes (identifiers are collected and stored in encrypted form)	All data extracted from EHR will be stored in the regulated environment	VACWM IS regulated environment
Recruitment – RMG	Smoker data will be collected from RMG EHR	Yes (identifiers are collected and stored in encrypted form)	All data extracted from EHR will be stored in the regulated environment	RMG IS regulated environment
Aims 2 and 3 Intervention				
Baseline and 1-week	In-person (baseline) and the phone	Yes (identifiers are collected and stored in encrypted form)	Will be directly entered into the UMMS database server in the regulated environment	UMMS IS regulated environment

